12.4.1 Individual Laboratory Measurements and Abnormal Laboratory Values

Table 12: Laboratory Adverse Event Grading Scale

Parameter	Mild (Grade 1)	Moderate (Grade 2)	Severe (Grade 3)
	Hematology		
WBC 10 ³ /μL (Decrease)	2.5 - 3.9	1.5 - 2.4	<1.5
WBC 10 ³ /μL (Increase)	10.6 – 15.0	15.1 - 20.0	>20.0
Hgb g/dL (Decrease) (Female)	10.1 – 11.4	8.5 - 10	<8.5
Hgb g/dL (Decrease) (Male)	11.0 – 12.4	9.5 - 10.9	<9.5
Platelets 10 ³ /μL (Decrease)	125 – 139	100 – 124	<100
Platelets 10 ³ /μL (Increase)	416 – 550	551-750	>750
	Chemistry		
ALT IU/L (Increase) (Female)	44 – 100	101 – 200	>200
ALT IU/L (Increase) (Male)	61 – 138	139 – 275	>275
Total Bilirubin mg/dL (Increase) – when accompanied by any increase in ALT	1.30 – 1.59	1.60 – 1.80	>1.80
Total Bilirubin mg/dL (Increase) – when ALT is normal	1.30 – 1.89	1.90 – 2.40	>2.40
Creatinine mg/dL (Increase) (Female)	1.1 – 1.7	1.8 – 2.0	>2.0
Creatinine mg/dL (Increase) (Male)	1.4 – 1.7	1.8 - 2.0	>2.0

14.1 Description of Study Subjects

14.1.1 Disposition of Subjects

Table 13: Subject Disposition by Study Arm

Subject	_	1 mg M-001 N=X)	-	B: Placebo =X)	All Su (N=	
Disposition	n	%	n	%	n	%
Screened					х	
Enrolled/Randomized	Х	100	х	100	х	100
Received Study Vaccination	Х	XX	х	XX	х	xx
Received first 2 doses	Х	XX	х	XX	х	xx
Received All Scheduled Study Vaccinations ^a	Х	XX	х	XX	х	xx
Completed PBMC Blood Draw at Study Day 43 (Visit 07)	х	xx	x	xx	х	XX
Completed Follow-up (Study Day 200) ^a	Х	XX	x	xx	х	xx
Completed Final PBMC Blood Draw (Day 200 / Visit 11)	X	XX	x	xx	X	xx

Note: N=Number of subjects enrolled.

^a Refer to Listing 2 for reasons subjects discontinued or terminated early.

Table 14: Analysis Populations by Study Arm

		Grou 1 mg l (N=	M-001	Plac	ip B: cebo =X)	All Su (N=	
Analysis Populations	Reason Subjects Excluded	n	%	n	%	%	n
Safety Analysis Population	Any Reason	х	xx	X	xx	х	xx
	No Study Vaccination Received						
Modified Intent-to-Treat Population	Any Reason						
	No Study Vaccination Received						
	Ineligible at Baseline						
	No Post-Vaccination Results Available						
Per Protocol, Day 9	Any Reason						
	No Study Vaccination Received						
	Ineligible at Baseline						
	No Day 9 Result Reported by Lab						
	Receipt of Non-Study Vaccination						
	Receipt of Immunosuppressive Medication						
	Day 9 Visit Out of Window						
Per Protocol, Day 15	Any Reason						
	No Study Vaccination Received						
	Ineligible at Baseline						
	No Day 15 Result Reported by Lab						
	Receipt of Non-Study Vaccination						
	Receipt of Immunosuppressive Medication						
	Day 15 Visit Out of Window						
Per Protocol, Day 22	Any Reason						
	No Study Vaccination Received						
	Ineligible at Baseline						
	No Day 22 Result Reported by Lab						
	Receipt of Non-Study Vaccination						
	Receipt of Immunosuppressive Medication						
	Day 22 Visit Out of Window						
Per Protocol, Day 30	Any Reason						
	No Study Vaccination Received						
	Study Vaccination 2 Not Received						
	Study Vaccination 2 Out of Window						
	Ineligible at Baseline						
	No Day 30 Result Reported by Lab						
	Receipt of Non-Study Vaccination						

Table 14: Analysis Populations by Study Arm (Continued)

		Grou 1 mg N (N=	M-001	Group B: Placebo (N=X)		All Subjects (N=X)	
Analysis Populations	Reason Subjects Excluded	n	%	n	%	%	n
	Receipt of Immunosuppressive Medication						
	Day 30 Visit Out of Window						
Per Protocol, Day 36 (Primary Endpoint)	Any Reason						
	No Study Vaccination Received						
	Study Vaccination 2 Not Received						
	Study Vaccination 2 Out of Window						
	Ineligible at Baseline						
	No Day 36 Result Reported by Lab						
	Receipt of Non-Study Vaccination						
	Receipt of Immunosuppressive Medication						
	Day 36 Visit Out of Window						
Per Protocol, Day 43	Any Reason						
	No Study Vaccination Received						
	Study Vaccination 2 Not Received						
	Study Vaccination 2 Out of Window						
	Ineligible at Baseline						
	No Day 43 Result Reported by Lab						
	Receipt of Non-Study Vaccination						
	Receipt of Immunosuppressive Medication						
	Day 43 Visit Out of Window						
Per Protocol, Day 78	Any Reason						
	No Study Vaccination Received						
	Study Vaccination 2 Not Received						
	Study Vaccination 2 Out of Window						
	Ineligible at Baseline						
	No Day 78 Result Reported by Lab						
	Receipt of Non-Study Vaccination						
	Receipt of Immunosuppressive Medication						
	Day 78 Visit Out of Window						
Per Protocol, Day 172	Any Reason						
	No Study Vaccination Received						
	Study Vaccination 2 Not Received						
	Study Vaccination 2 Out of Window						

Table 14: Analysis Populations by Study Arm (Continued)

		Group A: 1 mg M-001 (N=X)		Group B: Placebo (N=X)		All Subjects (N=X)	
Analysis Populations	Reason Subjects Excluded	n	%	n	%	%	n
	Ineligible at Baseline						
	No Day 172 Result Reported by Lab						
	Receipt of Non-Study Vaccination						
	Receipt of Immunosuppressive Medication						
	Day 172 Visit Out of Window						
Per Protocol, Day 186	Any Reason						
	No Study Vaccination Received						
	Study Vaccination 3 Not Received						
	Study Vaccination 3 Out of Window						
	Study Vaccination 2 Not Received						
	Study Vaccination 2 Out of Window						
	Ineligible at Baseline						
	No Day 186 Result Reported by Lab						
	Receipt of Non-Study Vaccination						
	Receipt of Immunosuppressive Medication						
	Day 186 Visit Out of Window						
Per Protocol, Day 200	Any Reason						
	No Study Vaccination Received						
	Study Vaccination 3 Not Received						
	Study Vaccination 3 Out of Window						
	Study Vaccination 2 Not Received						
	Study Vaccination 2 Out of Window						
	Ineligible at Baseline						
	No Day 200 Result Reported by Lab						
	Receipt of Non-Study Vaccination						
	Receipt of Immunosuppressive Medication						
	Day 200 Visit Out of Window						

Table 15: Dates of First Vaccination by Site and Study Arm

[Implementation Note: Weekly intervals for dosing date should be displayed. The earliest date should be the FSFV over all sites.]

Site 1: BCM		Site 2:	Iowa	Site 3: 0	ССНМС
Group A: 1 mg M-001 (N=X)	Group B: Placebo (N=X)	Group A: 1 mg M-001 (N=X)	Group B: Placebo (N=X)	Group A: 1 mg M-001 (N=X)	Group B: Placebo (N=X)
		Dose 1			
х	X	х	х	x	х
		Dose 2			
х	X	X	x	x	Х
		Dose 3			
х	x	x	x	x	х
	Group A: 1 mg M-001 (N=X)	Group A: 1 mg M-001 (N=X) Group B: Placebo (N=X) X X	Group A: 1 mg Group B: Placebo M-001 (N=X)	Group A: 1 mg Group B: Placebo M-001 (N=X) Dose 1	Group A: 1 mg Group B: Group A: 1 mg Hacebo M-001 (N=X) (N=X)

BCM=Baylor College of Medicine, Iowa=University of Iowa, CCHMC=Cincinnati Children's Hospital Medical Center

Table 16: Ineligibility Summary of Screen Failures

Inclusion/Exclusion Category	Inclusion/Exclusion Criterion	n ^a	% b
Inclusion and Exclusion	Number of subjects failing any eligibility criterion	X	100
Inclusion	Any inclusion criterion	x	XX
	Systolic blood pressure is within the per protocol range	x	XX
	Diastolic blood pressure is within the per protocol range	x	XX
	Are able to understand and comply with planned study procedures and be available for all study visits	x	XX
	Are in good health	X	XX
	Women of childbearing potential must use an acceptable method of contraception from 30 days prior to vaccination until 60 days after the second dose of M-001 or placebo	x	xx
	Women of childbearing potential must use an acceptable method of contraception from 30 days prior to receipt of IIV vaccination, and must plan to use until 28 days after the IIV	x	xx
Exclusion	Any exclusion criterion	x	XX
	Have any medical disease or condition that, in the opinion of the site PI or appropriate sub-investigator, is a contraindication to study participation	x	XX
	Have an acute illness, as determined by the site PI or appropriate sub-investigator, within 72 hours prior to study vaccination	x	xx
	Have signs or symptoms that could confound or confuse assessment of study vaccine reactogenicity	x	XX
	Plan to travel outside the U.S. (continental U.S., Hawaii, and Alaska) in the time between the first study vaccination and 21 days after the last study vaccination	x	XX
	Have been hospitalized for psychiatric illness, history of suicide attempt, or confinement for danger to self or others within 10 years prior to study vaccination	x	xx
	Blood donation or planned blood donation within 30 days prior to the study vaccination through 30 days after the last blood drawn for this study	x	xx
^a More than one criterion may be mark ^b Denominator for percentages is the t			

^b Denominator for percentages is the total number of screen failures.

14.1.2 Demographic Data by Study Group

Summary of Categorical Demographic and Baseline Characteristics by Site **Table 17:**

			: BCM =X)		2: Iowa =X)		CCHMC =X)	All Su (N=	bjects =X)
Variable	Characteristic	n	%	n	%	n	%	n	%
Sex	Male	х	XX	X	XX	x	xx	X	XX
	Female								
Ethnicity	Not Hispanic or Latino	x	XX	X	xx	х	XX	X	XX
	Hispanic or Latino								
	Not Reported								
	Unknown								
Race	American Indian or Alaska Native	x	XX	X	xx	х	XX	X	XX
	Asian								
	Native Hawaiian or Other Pacific Islander								
	Black or African American								
	White								
	Multi-Racial								
	Unknown								
Prior Seasonal Influenza Vaccination	2016-17 only								
	2017-18 only								
	Both								
	Neither								
	Unknown								
Age	18-29								
	30-39								
	40-49								
BMI	<30								
	≥30								
		•		•	•				

Notes: N=Number of subjects enrolled.
BCM=Baylor College of Medicine, Iowa=University of Iowa, CCHMC=Cincinnati Children's Hospital Medical Center

Summary of Continuous Demographic and Baseline Characteristics by Site **Table 18:**

Variable	Statistic	Site 1: BCM (N=X)	Site 2: Iowa (N=X)	Site 3: CCHMC (N=X)	All Subjects (N=X)
Age (Years)	Mean	xx	xx	xx	xx
	Standard Deviation	xx	xx	xx	xx
	Median	xx	xx	xx	xx
	Minimum	X	X	х	X
	Maximum	X	X	X	X
BMI	Mean	xx	xx	xx	xx
	Standard Deviation	xx	xx	xx	xx
	Median	xx	xx	xx	xx
	Minimum	X	X	X	X
	Maximum	x	X	x	X

Notes: N=Number of subjects enrolled.
BCM=Baylor College of Medicine, Iowa=University of Iowa, CCHMC=Cincinnati Children's Hospital Medical Center

Table 19: Summary of Categorical Demographic and Baseline Characteristics by Study Arm, All Enrolled Subjects

		Group A: (N	1 mg M-001 i=X)	Group B (N=	: Placebo =X)		bjects =X)
Variable	Characteristic	n	%	n	%	n	%
Sex	Male	X	XX	х	XX	Х	XX
	Female						
Ethnicity	Not Hispanic or Latino	X	XX	X	XX	X	XX
	Hispanic or Latino						
	Not Reported						
	Unknown						
Race	American Indian or Alaska Native	X	XX	X	xx	х	XX
	Asian						
	Native Hawaiian or Other Pacific Islander						
	Black or African American						
	White						
	Multi-Racial						
	Unknown						
Prior Seasonal Influenza Vaccination (2017-2018)	2016-17 only						
	2017-18 only						
	Both						
	Neither						
	Unknown						
Age	18-29						
	30-39						
	40-49						
BMI	<30						
	≥30						
Note: N=Number of subje	ects enrolled.	•	•	•	•	•	•

Table 20: Summary of Continuous Demographic and Baseline Characteristics by Study Arm, All Enrolled Subjects

Variable	Statistic	Group A: 1 mg M-001 (N=X)	Group B: Placebo (N=X)	All Subjects (N=X)
Age (years)	Mean	XX	XX	xx
	Standard Deviation	XX	XX	xx
	Median	X	X	X
	Minimum	X	X	X
	Maximum	X	Х	X
BMI	Mean	XX	XX	XX
	Standard Deviation	XX	XX	xx
	Median	X	X	X
	Minimum	X	Х	X
	Maximum	X	Х	X

14.1.3 Prior and Concurrent Medical Conditions

Table 21: Summary of Subjects with Pre-Existing Medical Conditions by MedDRA System Organ Class and Study Arm

	Group A: 1 (N	1 mg M-001 =X)		s: Placebo =X)	All Subjects (N=X)		
MedDRA System Organ Class	n	%	n	%	n	%	
Any SOC	Х	xx	х	xx	х	xx	
[SOC 1]							
[SOC 2]							

Notes: N=Number of subjects enrolled

n = Number of subjects reporting medical history within the specified SOC. A subject is only counted once per SOC.

14.2 Efficacy/Immunogenicity Data

Table 22: Geometric Mean Percentage (GMP) of CD4+ T Cell Subsets Expressing Markers Alone or in Combination After M-001 Stimulation with 95% Confidence Intervals by Study Day and Study Arm, Per Protocol Population*

Study	Dowf	CD107:	IFN-	TNF-	11.2	Gro	up A: 1 m	g M-001	(Group B:	Placebo	n realizar
Day	Perforin	CD107a	γ	α	IL2	n	GMP	95% CI	n	GMP	95% CI	p-value ^x
				•		Pri	imary End	lpoint				
Day 36	+	+	+	+	+	х	X.X	x.x, x.x	Х	X.X	X.X, X.X	
	+	+	+	+	-	х	X.X	x.x, x.x	Х	X.X	X.X, X.X	
	+	+	+	-	+	х	X.X	x.x, x.x	Х	X.X	X.X, X.X	
	+	+	+	-	-	х	X.X	x.x, x.x	Х	X.X	X.X, X.X	
	+	+	-	+	+	х	X.X	x.x, x.x	Х	X.X	X.X, X.X	
	+	+	-	+	-	х	X.X	x.x, x.x	Х	X.X	X.X, X.X	
	+	+	-	-	+	х	X.X	x.x, x.x	Х	X.X	X.X, X.X	
	+	+	-	-	-	х	X.X	x.x, x.x	Х	X.X	X.X, X.X	
	+	-	+	+	+	х	X.X	x.x, x.x	Х	X.X	X.X, X.X	
	+	-	+	+	-	х	X.X	x.x, x.x	Х	X.X	X.X, X.X	
	+	-	+	-	+	х	X.X	x.x, x.x	Х	X.X	X.X, X.X	
	+	-	+	-	-	х	X.X	x.x, x.x	Х	X.X	X.X, X.X	
	+	-	-	+	+	х	X.X	x.x, x.x	Х	X.X	X.X, X.X	
	+	-	-	+	-	х	x.x	x.x, x.x	Х	X.X	X.X, X.X	
	+	-	-	-	+	х	X.X	x.x, x.x	Х	X.X	X.X, X.X	
	+	-	-	-	-	х	X.X	x.x, x.x	Х	X.X	X.X, X.X	
	-	+	+	+	+	х	X.X	x.x, x.x	Х	X.X	X.X, X.X	
	-	+	+	+	-	х	X.X	x.x, x.x	Х	X.X	X.X, X.X	
	-	+	+	-	+	х	X.X	x.x, x.x	Х	X.X	X.X, X.X	
	-	+	+	-	-	х	X.X	x.x, x.x	Х	X.X	X.X, X.X	
	-	+	-	+	+	х	X.X	x.x, x.x	Х	X.X	X.X, X.X	
	-	+	-	+	-	х	X.X	x.x, x.x	Х	X.X	X.X, X.X	
	-	+	-	-	+	х	X.X	x.x, x.x	Х	X.X	X.X, X.X	
	-	+	-	-	-	х	X.X	x.x, x.x	Х	X.X	X.X, X.X	
	-	-	+	+	+	х	X.X	x.x, x.x	Х	X.X	X.X, X.X	
	-	-	+	+	-	х	X.X	x.x, x.x	X	X.X	X.X, X.X	
	-	-	+	-	+	х	X.X	x.x, x.x	Х	X.X	X.X, X.X	
	-	-	+	-	-	X	X.X	x.x, x.x	Х	X.X	X.X, X.X	
	-	-	-	+	+	х	X.X	x.x, x.x	Х	X.X	X.X, X.X	
	-	-	-	+	-	х	X.X	x.x, x.x	Х	X.X	X.X, X.X	
	-	-	-	-	+	Х	X.X	x.x, x.x	х	X.X	X.X, X.X	

Study	D. C.	CD107	IFN-	TNF-	11.2	Gro	up A: 1 m	g M-001	(Group B:	Placebo	
Day	Perforin	CD107a	γ	α	IL2	n	GMP	95% CI	n	GMP	95% CI	p-value ^x
	-	-	-	-	-	X	X.X	X.X, X.X	X	X.X	X.X, X.X	
	+	+/-	+/-	+/-	+/-	X	X.X	X.X, X.X	X	X.X	X.X, X.X	
	+/-	+	+/-	+/-	+/-	X	X.X	x.x, x.x	х	X.X	X.X, X.X	
	+/-	+/-	+	+/-	+/-	X	X.X	x.x, x.x	х	X.X	X.X, X.X	
	+/-	+/-	+/-	+	+/-	X	X.X	X.X, X.X	X	X.X	X.X, X.X	
	+/-	+/-	+/-	+/-	+	X	X.X	X.X, X.X	X	X.X	X.X, X.X	

Exploratory Endpoints

Repeat for Baseline, Day 15, Day 43, Day 78, Day 172, Day 186, and Day 200 without p-value column.

Notes: N = number of subjects in Per Protocol population.

Tables with similar format:

[Implementation Note: Do not include p-value column for Tables 28-31, and only include it for Day 36 for Tables 25-27. Include rows for any perforin, any CD107a, any IFN- γ , any TNF- α , and any IL2.]

- Table 23: Geometric Mean Percentage (GMP) of CD8+ T Cell Subsets Expressing Markers Alone or in Combination After M-001 Stimulation with 95% Confidence Intervals by Study Day and Study Arm, Per Protocol Population*
- Table 24: Geometric Mean Percentage (GMP) of CD4+ T Cell Subsets Expressing Markers Alone or in Combination After M-001 Stimulation with 95% Confidence Intervals by Study Day and Study Arm, Modified Intent-to-Treat Population*
- Table 25: Geometric Mean Percentage (GMP) Of CD8+ T Cell Subsets Expressing Markers Alone or in Combination After M-001 Stimulation with 95% Confidence Intervals by Study Day and Study Arm, Modified Intent-to-Treat Population*
- Table 26: Percentage of CD4+ T Cell Subsets Expressing Markers Alone or in Combination After Seasonal Influenza A Antigen Stimulation with 95% Confidence Intervals by Study Day and Study Arm, Per Protocol Population
- Table 27: Percentage of CD8+ T Cell Subsets Expressing Markers Alone or in Combination After Seasonal Influenza A Antigen Stimulation with 95% Confidence Intervals by Study Day and Study Arm, Per Protocol Population
- Table 28: Percentage of CD4+ T Cell Subsets Expressing Markers Alone or in Combination After Pandemic Influenza A Antigen Stimulation with 95% Confidence Intervals by Study Day and Study Arm, Per Protocol Population
- Table 29: Percentage of CD8+ T Cell Subsets Expressing Markers Alone or in Combination After Pandemic Influenza A Antigen Stimulation with 95% Confidence Intervals by Study Day and Study Arm, Per Protocol Population

^{*}Wald test from Poisson regression used to compare groups.

^{95%} CIs calculated via 10,000 bootstrap samples.

Table 30: Summaries of Hemagglutination Inhibition Antibody Against A/Michigan/45/2015 X-275 (H1N1) by Study Day and Study Arm, Per Protocol Population

	Group A: 1 mg M-001 (N=X)	Group B: Placebo (N=X)
Day 1		
n	x	X
GMT (95% CI)	xxx.x(xxx.x,xxx.x)	xxx.x(xxx.x,xxx.x)
Titer ≥ 1:40 - %(95% CI)	x.x (x.x, x.x)	x.x (x.x, x.x)
Day 22		
n	x	X
GMT (95% CI)	xxx.x(xxx.x,xxx.x)	xxx.x(xxx.x,xxx.x)
Seroconversion - %(95% CI)	x.x (x.x, x.x)	x.x (x.x, x.x)
Titer ≥ 1:40 - %(95% CI)	x.x (x.x, x.x)	x.x(x.x, x.x)
Day 43		
n	x	X
GMT (95% CI)	xxx.x(xxx.x,xxx.x)	xxx.x(xxx.x,xxx.x)
Seroconversion - %(95% CI)	x.x (x.x, x.x)	x.x(x.x, x.x)
Titer ≥ 1:40 - %(95% CI)	x.x (x.x, x.x)	x.x(x.x, x.x)
Day 172		
n	x	X
GMT (95% CI)	xxx.x(xxx.x,xxx.x)	xxx.x(xxx.x,xxx.x)
Seroconversion - %(95% CI)	x.x (x.x, x.x)	x.x (x.x, x.x)
Titer ≥ 1:40 - %(95% CI)	x.x (x.x, x.x)	x.x(x.x, x.x)
Day 200		
n	x	X
GMT (95% CI)	xxx.x(xxx.x,xxx.x)	xxx.x(xxx.x,xxx.x)
Seroconversion - %(95% CI)	x.x (x.x, x.x)	x.x (x.x, x.x)
Titer ≥ 1:40 - %(95% CI)	x.x (x.x, x.x)	x.x (x.x, x.x)

Tables with similar format:

- Table 31: Summaries of Hemagglutination Inhibition Antibody Against A/Singapore/INFIMH-16-0019/2016 NIB-104(H3N2)-Guinea RBC by Study Day and Study Arm, Per Protocol Population
- Table 32: Summaries of Hemagglutination Inhibition Antibody Against B/Colorado/6/2017 (B Victoria Lineage) by Study Day and Study Arm, Per Protocol Population
- Table 33: Summaries of Hemagglutination Inhibition Antibody Against B/Phuket/3073/2013 (B Yamagata Lineage) by Study Day and Study Arm, Per Protocol Population
- Table 34: Summaries of Neutralizing Antibody Against A/Michigan/45/2015 X-275 (H1N1) by Study Day and Study Arm, Per Protocol Population
- Table 35: Summaries of Neutralizing Antibody Against A/Singapore/INFIMH-16-0019/2016 NIB-104(H3N2) by Study Day and Study Arm, Per Protocol Population
- Table 36: Summaries of Neutralizing Antibody Against B/Colorado/6/2017 (B Victoria Lineage) by Study Day and Study Arm, Per Protocol Population
- Table 37: Summaries of Neutralizing Antibody Against B/Phuket/3073/2013 (B Yamagata Lineage) by Study Day and Study Arm, Per Protocol Population

Table 38: Percentage of Influenza-Specific CD4+ Cell Subsets Expressing Discrete Memory Markers (CCR7, CD45RO, and CD57) by Study Arm and Study Day, Per Protocol Population

				(Froup A: 1 mg	g M-001		Group B: P	lacebo
Study Day	CCR7	CD45RO	CD57	n	GMP	95% CI	n	GMP	95% CI
Baseline	+	+	+	х	X.X	x.x, x.x	Х	X.X	x.x, x.x
	+	+	-	х	X.X	x.x, x.x	х	X.X	x.x, x.x
	+	-	-	х	X.X	X.X, X.X	Х	X.X	x.x, x.x
	+	-	+	х	X.X	x.x, x.x	х	X.X	x.x, x.x
	-	+	+	х	X.X	X.X, X.X	Х	X.X	x.x, x.x
	-	+	-	х	X.X	X.X, X.X	Х	X.X	x.x, x.x
	-	-	+	х	X.X	X.X, X.X	Х	X.X	x.x, x.x
	-	-	-	х	X.X	X.X, X.X	х	X.X	X.X, X.X
	+	+/-	+/-	х	X.X	x.x, x.x	Х	X.X	x.x, x.x
	+/-	+	+/-	х	X.X	X.X, X.X	х	X.X	X.X, X.X
	+/-	+/-	+	х	X.X	x.x, x.x	Х	X.X	X.X, X.X
Day 15	+	+	+	х	X.X	x.x, x.x	Х	X.X	X.X, X.X
	+	+	-	х	X.X	X.X, X.X	Х	X.X	x.x, x.x
	+	-	-	х	X.X	X.X, X.X	Х	X.X	x.x, x.x
	+	-	+	х	X.X	X.X, X.X	Х	X.X	X.X, X.X
	-	+	+	х	X.X	X.X, X.X	Х	X.X	x.x, x.x
	-	+	-	х	X.X	X.X, X.X	Х	X.X	x.x, x.x
	-	-	+	х	X.X	X.X, X.X	Х	X.X	x.x, x.x
	-	-	-	х	X.X	X.X, X.X	Х	X.X	x.x, x.x
	+	+/-	+/-	х	X.X	X.X, X.X	Х	X.X	x.x, x.x
	+/-	+	+/-	х	X.X	x.x, x.x	Х	X.X	x.x, x.x
	+/-	+/-	+	х	X.X	X.X, X.X	Х	X.X	X.X, X.X
Day 36	+	+	+	х	X.X	X.X, X.X	Х	X.X	X.X, X.X
	+	+	-	х	X.X	X.X, X.X	Х	X.X	x.x, x.x
	+	-	-	х	X.X	X.X, X.X	Х	X.X	X.X, X.X
	+	-	+	х	X.X	X.X, X.X	Х	X.X	X.X, X.X
	-	+	+	х	X.X	x.x, x.x	Х	X.X	x.x, x.x
	-	+	-	х	X.X	x.x, x.x	х	X.X	x.x, x.x
	-	-	+	х	X.X	x.x, x.x	Х	X.X	x.x, x.x
	-	-	-	х	X.X	x.x, x.x	Х	X.X	x.x, x.x
	+	+/-	+/-	х	X.X	x.x, x.x	х	X.X	x.x, x.x
	+/-	+	+/-	х	X.X	x.x, x.x	Х	X.X	x.x, x.x
	+/-	+/-	+	х	X.X	x.x, x.x	Х	X.X	x.x, x.x

Table 38: Percentage of Influenza-Specific CD4+ Cell Subsets Expressing Discrete Memory Markers (CCR7, CD45RO, and CD57) by Study Arm and Study Day, Per Protocol Population (Continued)

				G	roup A: 1 mg	M-001		Group B:	Placebo
Study Day	CCR7	CD45RO	CD57	n	GMP	95% CI	n	GMP	95% CI
Day 43	+	+	+	Х	X.X	X.X, X.X	х	X.X	X.X, X.X
	+	+	-	Х	X.X	X.X, X.X	х	X.X	X.X, X.X
	+	-	-	Х	X.X	X.X, X.X	х	X.X	X.X, X.X
	+	-	+	Х	X.X	X.X, X.X	х	X.X	X.X, X.X
	-	+	+	Х	X.X	X.X, X.X	х	X.X	X.X, X.X
	-	+	-	Х	X.X	X.X, X.X	х	X.X	X.X, X.X
	-	-	+	Х	X.X	X.X, X.X	х	X.X	X.X, X.X
	-	-	-	Х	X.X	X.X, X.X	х	X.X	X.X, X.X
	+	+/-	+/-	Х	X.X	X.X, X.X	х	X.X	X.X, X.X
	+/-	+	+/-	Х	X.X	X.X, X.X	х	X.X	X.X, X.X
	+/-	+/-	+	Х	X.X	X.X, X.X	х	X.X	X.X, X.X
Day 78	+	+	+	Х	X.X	X.X, X.X	х	X.X	X.X, X.X
	+	+	-	Х	X.X	X.X, X.X	х	X.X	X.X, X.X
	+	-	-	Х	X.X	X.X, X.X	х	X.X	X.X, X.X
	+	-	+	Х	X.X	X.X, X.X	х	X.X	X.X, X.X
	-	+	+	Х	X.X	X.X, X.X	х	X.X	X.X, X.X
	-	+	-	Х	X.X	X.X, X.X	х	X.X	X.X, X.X
	-	-	+	X	X.X	X.X, X.X	х	X.X	X.X, X.X
	-	-	-	Х	X.X	X.X, X.X	х	X.X	X.X, X.X
	+	+/-	+/-	Х	X.X	X.X, X.X	х	X.X	X.X, X.X
	+/-	+	+/-	Х	X.X	X.X, X.X	х	X.X	X.X, X.X
	+/-	+/-	+	Х	X.X	X.X, X.X	х	X.X	X.X, X.X
Day 172	+	+	+	Х	X.X	X.X, X.X	х	X.X	X.X, X.X
	+	+	-	X	X.X	X.X, X.X	х	X.X	X.X, X.X
	+	-	-	Х	X.X	X.X, X.X	х	X.X	X.X, X.X
	+	-	+	Х	X.X	X.X, X.X	Х	X.X	X.X, X.X
	-	+	+	Х	X.X	X.X, X.X	Х	X.X	X.X, X.X
	-	+	-	х	X.X	x.x, x.x	х	X.X	X.X, X.X
	-	-	+	Х	X.X	X.X, X.X	Х	X.X	X.X, X.X
	-	-	-	Х	X.X	X.X, X.X	Х	X.X	X.X, X.X
	+	+/-	+/-	Х	X.X	X.X, X.X	Х	X.X	X.X, X.X
	+/-	+	+/-	Х	X.X	X.X, X.X	Х	X.X	X.X, X.X
	+/-	+/-	+	X	X.X	X.X, X.X	X	X.X	X.X, X.X
Day 186	+	+	+	X	X.X	x.x, x.x	х	X.X	X.X, X.X

Table 38: Percentage of Influenza-Specific CD4+ Cell Subsets Expressing Discrete Memory Markers (CCR7, CD45RO, and CD57) by Study Arm and Study Day, Per Protocol Population (Continued)

				G	roup A: 1 mg	M-001	Group B: Placebo			
Study Day	CCR7	CD45RO	CD57	n	GMP	95% CI	n	GMP	95% CI	
	+	+	-	х	X.X	x.x, x.x	х	X.X	x.x, x.x	
	+	-	-	х	X.X	x.x, x.x	х	X.X	X.X, X.X	
	+	-	+	х	X.X	x.x, x.x	Х	X.X	x.x, x.x	
	-	+	+	х	X.X	x.x, x.x	Х	X.X	x.x, x.x	
	-	+	-	х	X.X	x.x, x.x	х	X.X	x.x, x.x	
	-	-	+	х	X.X	x.x, x.x	Х	X.X	x.x, x.x	
	-	-	-	х	X.X	x.x, x.x	Х	X.X	X.X, X.X	
	+	+/-	+/-	X	X.X	x.x, x.x	х	X.X	X.X, X.X	
	+/-	+	+/-	X	X.X	x.x, x.x	х	X.X	X.X, X.X	
	+/-	+/-	+	Х	X.X	x.x, x.x	Х	X.X	X.X, X.X	
Day 200	+	+	+	X	X.X	x.x, x.x	X	X.X	X.X, X.X	
	+	+	-	Х	X.X	x.x, x.x	Х	X.X	X.X, X.X	
	+	-	-	X	X.X	x.x, x.x	X	X.X	x.x, x.x	
	+	-	+	Х	X.X	x.x, x.x	Х	X.X	X.X, X.X	
	-	+	+	Х	X.X	x.x, x.x	Х	X.X	X.X, X.X	
	-	+	-	Х	X.X	x.x, x.x	Х	X.X	X.X, X.X	
	-	-	+	х	X.X	x.x, x.x	Х	X.X	X.X, X.X	
	-	-	-	х	X.X	x.x, x.x	Х	X.X	x.x, x.x	
	+	+/-	+/-	х	X.X	x.x, x.x	Х	X.X	x.x, x.x	
	+/-	+	+/-	х	X.X	x.x, x.x	Х	X.X	x.x, x.x	
	+/-	+/-	+	х	X.X	x.x, x.x	х	X.X	x.x, x.x	

Tables with similar format:

- Table 39: Percentage of Influenza-Specific CD8+ Cell Subsets Expressing Discrete Memory Markers (CCR7, CD45RO, and CD57) by Study Arm and Study Day, Per Protocol Population
- Table 40: Percentage of Influenza-Specific CD4+ Cell Subsets expressing IL-4 or IL-17 by Study Arm and Study Day, Per Protocol Population
- Table 41: Percentage of Influenza-Specific CD4+ Cell Subsets expressing T Follicular Helper Cells (CD4+, CXCR5+, PD-1+, IL-21+) by Study Arm and Study Day, Per Protocol Population
- Table 42: Percentage of Influenza-Specific CD4+ Cell Subsets expressing T Follicular Regulatory Cells (CXCR5+, PD-1+, CD25+, CD127+) by Study Arm and Study Day, Per Protocol Population
- Table 43: Percentage of Influenza-Specific CD4+ Cell Subsets expressing Tregs (CD25+, Foxp3+) by Study Arm and Study Day, Per Protocol Population

Table 44: Summaries of ELISA Antibody Against M-001 by Study Day and Study Arm, Per Protocol Population

		Group A: 1 mg M-00)1		Group B: Placebo					
Study Day	N	GMT (95% CI)	Seroconversion % (95% CI)	N	GMT (95% CI)	Seroconversion % (95% CI)				
Baseline	X	x.x (x.x, x.x)	NA	Х	x.x (x.x, x.x)	NA				
Day 22	х	x.x (x.x, x.x)	xx (xx, xx)	Х	x.x (x.x, x.x)	xx (xx, xx)				
Day 43	х	x.x (x.x, x.x)	xx (xx, xx)	Х	x.x (x.x, x.x)	xx (xx, xx)				
Day 78	х	x.x (x.x, x.x)	xx (xx, xx)	Х	x.x (x.x, x.x)	xx (xx, xx)				
Day 172	х	x.x (x.x, x.x)	xx (xx, xx)	Х	x.x (x.x, x.x)	xx (xx, xx)				
Day 200	x	x.x (x.x, x.x)	xx (xx, xx)	Х	x.x (x.x, x.x)	xx (xx, xx)				

Notes: N=Number of subjects in Per Protocol population.

Seroconversion is defined as either a pre-vaccination titer < 10 and a post-vaccination titer ≥ 40 or a pre-vaccination titer ≥ 10 and a minimum four-fold rise in post-vaccination antibody titer.

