11.5.3. Humoral Immunogenicity Data

Summaries and analysis of immunogenicity data will be presented for the ITT and PP populations; the PP population will be considered the primary analysis.

Immune responses in terms of strain-specific (IIV4 strains) HAI and Neut antibody titers will be summarized by treatment arm at each time point. Analyses at all time points will include proportion of subjects with titers ≥ 40 and geometric mean titers (GMTs). Additionally the proportion of subjects achieving seroconversion from Day 172 to Day 200 (defined as either a pre-vaccination titer < 10 and a post-vaccination titer ≥ 40 or a pre-vaccination titer ≥ 10 and a minimum four-fold rise in post-vaccination antibody titer) will be presented. All summaries will include the corresponding 95% confidence intervals.

The proportion of subjects with seroconversion from Day 172 to 200 will be compared to evaluate the effect of M-001 priming using a two-sided Likelihood Ratio Test.

M-001 antibody response will be summarized by GMTs the proportion of subjects achieving seroconversion (defined as a minimum four-fold rise in post-vaccination ELISA antibody titer) at each time point, with corresponding 95% confidence intervals.

The correlation between HAI, Neut, and M-001 antibody titers will be evaluated. Plots such as reverse cumulative distributions or longitudinal presentations of GMTs will be presented for each assay.

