3.2.3. Exploratory Outcome Measures

Immunogenicity

- Percentage of subjects achieving seroconversion (defined as a minimum four-fold rise in post-vaccination ELISA antibody titer) and GMTs of ELISA antibody vs. M-001 from Day 1 to Days 22, 43, 78, 172 and 200
- Geometric Mean Percentage of T cell subsets expressing perforin, CD107a, IFN-γ, TNF-α, and IL2, alone or in combination in CD4 and CD8 cells after stimulation with M-001 peptides at baseline (Day 1) and approximately 14 days after one dose of M-001, 56 days following the second dose of M-001, and immediately prior to and 14 and 28 days after IIV4
- Percentage of T cell subsets expressing perforin, CD107a, IFN-γ, TNF-α, and IL2, alone or in combination, in CD4 and CD8 cells after stimulation with other influenza A antigens (including

seasonal and pandemic influenza antigens) at baseline (Day 1), approximately 14 days after each study vaccination, 56 days following the second study vaccination and immediately prior to and approximately 28 days after IIV4

 Percentage of influenza-specific T cell memory subsets expressing discrete memory markers (CCR7, CD45RO, and CD57) at baseline (Day 1), approximately 56 days after the second dose of placebo or M-001 and immediately prior to and approximately 28 days after the IIV4 dose

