3.3. Study Definitions and Derived Variables

Geometric mean percentages (GMPs) are calculated as the product of the observed percentages raised to the 1/Nth root, where N is the number of observed values.

The baseline value for cellular and humoral immunity will be defined as the value obtained on Day 1 prior to M-001 vaccination.

M-001 antibody response after baseline will be summarized by GMTs and the proportion of subjects achieving seroconversion (defined as a minimum four-fold rise in post-vaccination ELISA antibody titer) at each time point, with corresponding 95% confidence intervals.

For individual subjects, fold rise will be calculated as the ratio of: $\frac{post-vaccination\ titer}{pre-vaccination\ titer}$, where pre-vaccination value is always the result obtained at Day 1, prior to the first M-001 dose.

Seroconversion for HAI and Neut assays is defined as either a pre-vaccination titer < 1:10 and a post-vaccination titer $\ge 1:40$, or a pre-vaccination titer $\ge 1:10$ and a minimum four-fold rise in post-vaccination titer.

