4.5.2. Immunogenicity Variables

Cellular immunogenicity data will be reported by the Baylor College of Medicine. These data will include the frequency of influenza-specific T cells as measured by fluorescence-based flow cytometric assays. The lab at Baylor will also report the percentage of influenza-specific T cells expressing discrete memory markers (CCR7, CD45RO, and CD57), the percentage of CD4 and CD8 T cells expressing perforin, CD107a, IFN- γ , TNF- α , and IL2, alone or in combination, the percentage of CD4+ T cell subsets expressing IL-4 or IL-17, T follicular helper (TFH) cells (CD4+, CXCR5+, PD-1+, IL-21+) , T follicular regulatory (Tfr) cells (CXCR5+, PD-1+, CD25+, CD127+) , and T regulatory cells (Tregs) (CD25+, Foxp3+)as measured by flow cytometry.

Individual HAI and Neut antibody results will be reported for the IIV4 vaccine strain by the central immunology laboratory at St Louis University. Assay results are reported as a reciprocal titer with values of $10*2^k$, where k=0, 1, 2, etc. The lower limit of detection for both the HAI and Neut assays is 1:10; values below the limit of detection are reported as '<10', and for analysis are imputed as one-half the limit of detection (10/2 = 5). For analysis, the geometric mean of repeated results for each sample will be computed and used as the response for all subsequent calculations. The variation arising from multiple measurements for an individual at a single time point will not be used in subsequent calculations. See Section 3.3 for definitions of derived variables for the analysis of HAI and Neut data.

Assays to determine serum levels of antibodies to M-001 will be performed by BiondVax.

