8.3. Exploratory Immunogenicity Analyses

ELISA seroconversion and GMTs of the ELISA antibody against M-001 from Day 1 to Days 22, 43, 78, 172, and 200 will be presented in Table 44.

Table 26Table 27Table 28Table 29

These percentages will be summarized visually in box plots over time in Figure 6, Figure 7, Figure 8, and Figure 9, for selected cell subsets.

GMPs of influenza-specific CD4+ T cell subsets expressing discrete memory markers (CCR7, CD45RO, and CD57) will be summarized at baseline (Day 1) and on study days 15, 36, 43, 78, 172, 186, and 200 (Table 38), by study arm. The subject-level percentages corresponding to selected cell subsets will be presented in Figure 30. Analogous summaries will be presented for CD8+ T cells in Table 39and Figure 31.

The percentage of influenza-specific CD4+ cell subsets expressing IL-4 or IL-17, T follicular helper cells (CD4+, CXCR5+, PD-1+, IL-21+), T follicular regulatory (Tfr) cells (CXCR5+, PD-1+, CD25+, CD127+), and Tregs (CD25+, Foxp3+) measured by flow cytometry will be summarized at baseline (Day 1) and on study days 15, 36, 43, 78, 172, 186, and 200 (Table 40, Table 41, Table 42, and Table 43, respectively). Boxplots for these percentages will also be presented in Figure 32, Figure 33, Figure 34, and Figure 35.

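### The Table 44 footnote defines M-001 ELISA seroconversion by the HAI/Neut rule, while the endpoint is a four-fold rise; following the shell can only lower the ELISA responder rate or leave it unchanged

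*SAP*

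**What the plan says.** Four sections give one rule for the M-001 ELISA. SAP section 3.3 summarises the antibody response by GMT and by the proportion "achieving seroconversion (defined as a minimum four-fold rise in post-vaccination ELISA antibody titer) at each time point". SAP section 3.2.3 and Protocol section 3.2.3 use the same definition for the exploratory outcome measure, and so does the analysis text in Protocol section 11.5.3. None of them has a branch for low starting titers. SAP section 3.3 fixes the reference for fold rise at Day 1, before the first M-001 dose.

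SAP section 3.3 assigns the two-part rule to other assays by name: "Seroconversion for HAI and Neut assays is defined as either a pre-vaccination titer < 1:10", followed by the titer of 40 and the four-fold branch.

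SAP section 8.3 sends "ELISA seroconversion and GMTs of the ELISA antibody against M-001 from Day 1 to Days 22, 43, 78, 172, and 200" to Table 44. The footnote under that shell (Appendix 1, under 14.2 Efficacy/Immunogenicity Data) reads "Seroconversion is defined as either a pre-vaccination titer < 10 and a post-vaccination titer ≥ 40" and continues with the four-fold branch for starting titers of 10 or more.

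SAP section 12 lists two departures from the protocol: the Poisson model for the primary analysis, and restriction of the mITT population to a sensitivity analysis. The ELISA definition is not among them.

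**The concern.** The shell that will carry the ELISA responder rate states a rule that belongs to different assays and contradicts the endpoint definition. A footnote in a table shell guides the programming and is also printed with the result, so there are two ways to go wrong. If the programmer follows the footnote, the table reports a different endpoint. If the programmer follows section 3.3, the table is right but its label tells the reader otherwise.

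The cut-offs of 10 and 40 also have no stated basis for this assay. SAP section 4.5.2 says "The lower limit of detection for both the HAI and Neut assays is 1:10" and gives the value 5 for results below it, for those two assays only. For the ELISA it says only who runs the assay.

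**Working it through.** The plan states no ELISA responder rate, power or sample size, so there is no figure to reproduce. The check compares the two rules directly.

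**Inputs.** Endpoint rule: post/b ≥ 4, where b is the Day 1 titer (SAP sections 3.2.3 and 3.3; Protocol sections 3.2.3 and 11.5.3). Footnote rule: post ≥ 40 if b < 10; post/b ≥ 4 if b ≥ 10 (Table 44). Arm size: 60 (SAP section 4.1). Coding of values below 10 as 5: stated for HAI and Neut in SAP section 4.5.2, and carried to the ELISA here only as an assumption.

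**Step 1: b ≥ 10.** Both rules require post ≥ 4b, so they cannot disagree.

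**Step 2: b < 10.** The endpoint requires post ≥ 4b and the footnote requires post ≥ 40. Since 4b < 40, the footnote is the stricter rule. A subject is a responder under the endpoint but not under the footnote when 4b ≤ post < 40. The reverse cannot happen.

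**Step 3: examples.** The last column uses the two-fold titer series 5, 10, 20, 40 and so on.

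| Day 1 value b | Endpoint threshold 4b | Footnote threshold | Fold rise the footnote demands (40/b) | Titers on which the rules disagree |
|---|---|---|---|---|
| 2.5 | 10 | 40 | 16 | 10, 20 |
| 5 | 20 | 40 | 8 | 20 |
| 8 | 32 | 40 | 5 | none on this series |
| 10 | 40 | 40 | 4 | none |

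With the assumed coding at 5, the footnote asks for an 8-fold rise where the endpoint asks for 4-fold. If values below 10 were coded 10 instead, the two rules would coincide.

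**Step 4: effect on an arm.** Let q be the share of the arm with a Day 1 value below 10, and r the share of those whose later titer lies from 20 to below 40 (coding at 5 assumed). The responder rate falls by q × r. Neither share is in the documents, so the following is an assumed range with n = 60:

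- q = 0: 0 points, 0 subjects.
- q = 0.25, r = 0.2: 0.25 × 0.2 = 5 points; 60 × 0.05 = 3 subjects.
- q = 0.5, r = 0.2: 0.5 × 0.2 = 10 points; 60 × 0.10 = 6 subjects.
- q = 1, r = 0.3: 1 × 0.3 = 30 points; 60 × 0.30 = 18 subjects.

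These figures show how the effect scales. They do not estimate it.

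**The case against.** The strongest reply is that this is a clerical slip with little practical risk. The definitions section and the outcome measure are explicit, agree with each other and agree with the protocol. The endpoint is exploratory and is summarised with confidence intervals, with no planned comparison between arms. Much of this stands: the point is an inconsistency in a shell, not a dispute over method. It does not remove the need for a correction, because the SAP does not say whether text or shell prevails, and a correctly programmed table would still carry the wrong label.

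A reader might infer more than the documents support, in three ways.

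- That Table 44 will report a different rate. This needs Day 1 ELISA values below 10 and later titers from 4b to below 40. Nothing in the documents shows that the ELISA yields values below 10 at all.
- That the rate would be roughly halved. Suppose the log2 rise among subjects below 10 is normal with SD 1.5, and values below 10 are coded 5. A mean rise of 2 then gives 50% under the four-fold rule (log2 rise at least 2) and 25% under the footnote (at least 3). A mean of 6 gives 99.6% and 97.7%. Mean, SD and coding are all assumed, and the figures apply only to a subgroup whose share is unknown and may be zero.
- That the loss falls on antibody-naive subjects, in whom the response is clearest. The documents do not equate an ELISA value below 10 with lack of prior antibody, nor say who responds most. With no stated ELISA scale, 10 cannot serve as that marker.

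**Conclusion.** The footnote is wrong as written: it contradicts a definition given consistently in both documents, and no recorded change explains it. The direction of any error is certain from the rules alone, since the footnote can only reduce the number of ELISA responders or leave it the same, and only among subjects with a Day 1 value below 10. The size cannot be determined from the documents and may be zero. The 8-fold figure rests on borrowing the HAI/Neut coding of 5.

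The reach is narrow. Only the seroconversion columns of Table 44 are exposed. The ELISA GMTs in that table do not use the rule, and HAI and Neut seroconversion is reported in Tables 30 to 37 under its own definition. This is a minor point, worth correcting because the correction is so small.

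**What to change.** Replace the Table 44 footnote with: *Seroconversion is a rise of at least four-fold in M-001 ELISA antibody titer from Day 1.* This matches SAP section 3.3 and the protocol. The cost is one footnote; no new data or analysis is needed.

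It would help to add a sentence to SAP section 4.5.2 giving the ELISA detection limit, if there is one, and how values below it are handled, because a fold rise from such a value depends on that choice. The footnote change removes the contradiction without it.
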